QBA is a form of sensitivity analysis that aims to quantify and adjust for systematic errors and the uncertainty about these errors.²⁰ An important benefit of using QBA is that it makes assumptions regarding the structure and impact of the bias explicit and reduces overconfidence in research findings.^{21–23} Despite having first been described decades ago,^{22,24–26} QBA has so far rarely been applied to epidemiologic studies^{26,27}, which may in part be due to a lack of guidance on which methods to apply and how best to apply them.^{20,28,29} QBA can be applied to many types of biases that may arise in pharmacoepidemiologic studies, such as exposure and outcome misclassification, selection bias and confounding. For example, misclassification of drug exposures may arise in EHRs due to stockpiling of medication, patients not filling prescriptions, non-adherence, or underascertainment of in-hospital medication use. Using COVID-19 infection as an outcome may be subject to misclassification due to non-random testing and limited testing availability. Non-random testing may result in selection bias where testing is a condition of entry into the study population. Selection bias may also arise in the form of collider bias if study populations have been restricted to people experiencing an event such as COVID-19 testing or hospitalisation.³⁰

Confounding can occur as confounding by indication when clinical indication influences the exposure, i.e., treatment, and the outcome under investigation. While using an active comparator can reduce confounding by indication, there is no perfect active comparator in asthma or COPD, and the reasons for choosing a specific treatment regimen are not always known.

Studies investigating the impact of ICS on COVID-19 outcomes have so far given conflicting results. ICS may have different effects at different stages of the COVID-19 disease pathway from infection to hospitalisation and death. It can therefore be difficult to compare results between studies when there are differences in study design and differences in timing of drug administration, and the populations studied.¹⁹ However, the inconsistent findings may also be in part due to biases affecting the studies, including for example bias due to imperfect and incomplete ascertainment of SARS-CoV-2 infections or misclassification of ICS exposures. This study will use ICS as a “case study” to investigate the application of QBA in pharmacoepidemiologic studies of COVID-19.

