The COPD cohort will include all adults aged 35 and over with a recorded diagnosis of COPD at any point before the cohort entry date.⁴¹ This method of identifying COPD has previously been validated in CPRD.⁴¹ Code lists to identify COPD will be reviewed by a clinical expert before use. To be included, patients must also have a record of current or former smoking in CPRD.

As in the asthma cohort, patients who have a record of other chronic respiratory conditions at any point before the cohort entry date will be excluded. People who use a leukotriene receptor antagonist (LTRA) within 3 years of the cohort entry date will be excluded as this indicates asthma, as will people who are prescribed a LABA/LAMA and ICS within 3 months before the cohort entry date, as this indicates severe COPD.

Censoring

For all cohorts, cohort exit will be defined as the first of either occurrence of the outcome (for each analysis), death, disenrollment from GP practice, the last date of data availability, or the end of the COVID-19 wave (31st August 2020 for wave 1, 30th April 2021 for wave 2).

M. Comparator groups

The study will use an active comparator group including all people with recorded asthma within 3 years or COPD at any point before the cohort entry date (1st March 2020 or 1st September 2020, respectively) who received a prescription for inhaled medication for asthma or COPD, but no ICS prescription.

The comparator group for the asthma cohort will be people who were not prescribed medication containing ICS and were prescribed a non-ICS inhaled medication for asthma. For the COPD cohort, the comparator group will include people who were not prescribed a medication containing ICS and were prescribed a LABA/LAMA separately or in combination for COPD. Exposures and exposure durations in the comparator group will be calculated in the same way as in the ICS-exposed group.

N. Exposures, outcomes and covariates

Exposure

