Exposure will be prescription of ICS, which may be determined in a time-fixed or time-updated manner. Which method of exposure ascertainment will be chosen will be informed by the findings of the descriptive study of prescription patterns. For example, if we observe a significant increase in prescriptions for ICS at the start of the pandemic (March 2020) in the descriptive study, suggesting stockpiling occurred, it may be difficult to ascertain the end of an exposure period. While a time-updated approach would be more accurate and preferable in theory, a time-fixed exposure definition may be preferable if exposure periods cannot be estimated with confidence, for example due to stockpiling. The descriptive study will be completed before the start of the analyses of the comparative studies.

- **Time-fixed exposure:** prescription of ICS within 3 months before the cohort entry date (1st March 2020 for wave 1, 1st September 2020 for wave 2), and the comparator group as people who did not receive a prescription for ICS within the 3 months before the cohort entry date, but did receive a prescription for another inhaled medication for COPD or asthma. Patients can then not switch between exposure groups, even if they initiate ICS or their ICS exposure ends, analogous to an “intention to treat” approach.
- **Time-updated exposure:** ICS prescriptions in the year before the cohort entry date up until the end of follow-up will be used to ascertain exposure status throughout the follow-up time. Length of exposure for each prescription will be calculated by multiplying the quantity by any relevant dose information stored in the packtype variable and dividing by the value in the numeric daily dose variable. Where it is not possible to calculate the exposure period, the median prescription length for that drug might be imputed as the exposure duration.⁴² An allowable gap between the end of a calculated drug supply and receipt of a new prescription would be permitted, e.g. half a median exposure duration. Where one prescription is issued

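### The COPD comparator is stated inconsistently: one sentence requires a LABA or LAMA, two others accept any non-ICS inhaler, and no look-back window is stated for the comparator drug

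*Protocol*

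**What the plan says.** The protocol describes the comparator in three places.

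- **Section M, opening paragraph, both diseases:** people with asthma or COPD "who received a prescription for inhaled medication for asthma or COPD, but no ICS prescription".
- **Section M, by cohort:** the COPD comparator is people "not prescribed a medication containing ICS and were prescribed a LABA/LAMA separately or in combination for COPD". The asthma comparator is people who "were not prescribed medication containing ICS and were prescribed a non-ICS inhaled medication for asthma".
- **Section N, time-fixed exposure, both diseases in one rule:** the first condition describes "people who did not receive a prescription for ICS within the 3 months before the cohort entry date". The second condition, on what these patients were given instead, reads "but did receive a prescription for another inhaled medication for COPD or asthma".

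Section M closes by saying that exposure and its duration are worked out for comparators as they are for ICS users. Section C gives the purpose of the design and its limits: "While using an active comparator can reduce confounding by indication, there is no perfect active comparator in asthma or COPD". Section P names severity of the underlying respiratory disease as a likely key source of unmeasured confounding.

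**The concern.** For asthma the statements agree. For COPD they do not: a patient whose only inhaler is a short-acting reliever is a comparator under section N and under section M's opening paragraph, but not under section M's COPD sentence. Two programmers could build different COPD comparators, and each could cite the protocol.

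The comparator fixes what every COPD hazard ratio means. If reliever-only patients differ in severity from patients on maintenance inhalers, admitting them undoes part of what the active comparator is for. The only COPD-specific severity covariate listed in section N is the number of exacerbations in the prior year, so weighting may not remove a difference in treatment step.

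The bias analysis in section P is affected too. It needs the association between severe disease and ICS exposure, and that quantity changes with who is in the comparator.

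**Working it through.** **1. Who qualifies.** Consider a COPD patient with no ICS.

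| Inhaler | M, opening | M, COPD sentence | N, time-fixed |
|---|---|---|---|
| LABA and/or LAMA | yes | yes | yes |
| Short-acting reliever only | yes | no | yes |

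Cohort entry in section L does not settle the second row. It asks for a COPD code, age 35 or over and a smoking record, but not for maintenance therapy.

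**2. Look-back window.** Section N attaches its 3 months to the absence of ICS and states no window for the other inhaler. Section M states none for the LABA/LAMA. Its closing sentence implies the ICS window but does not say so.

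**3. Possible size.** The documents give neither the reliever-only share nor the relative hazard, so both are assumptions. Let s be the reliever-only share of the comparator and r their hazard relative to LABA/LAMA users. With a true hazard ratio of 1 against LABA/LAMA, and before adjustment, approximately:

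observed HR = 1 / (1 − s + s·r)

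- s = 0.10, r = 0.8: 1/0.98 = 1.02
- s = 0.30, r = 0.6: 1/0.88 = 1.14
- s = 0.40, r = 0.5: 1/0.80 = 1.25
- any s, r = 1: 1.00
- s = 0.25, r = 1.25: 1/1.0625 = 0.94

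Over s = 0.10 to 0.60 and r = 0.5 to 1.25 the result runs from 0.87 to 1.43. With section M's COPD definition s = 0, and the result is 1.00.

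**4. Cost in power.** First, the plan's own figure. Table 1 gives 204,965 for HR 1.2 at an outcome probability of 0.5% with 64% on ICS. Events = (1.960 + 0.842)² / (0.64 × 0.36 × (ln 1.2)²) = about 1,024.8, and 1,024.8/0.005 = 204,965. The figure reproduces and does not depend on the disputed wording.

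Next, the COPD cohort for a positive test. Section J gives 225,472 patients, of whom 83,668 had ICS, leaving 141,804 without. Section K gives an outcome probability of 0.52%. With D events and ICS share a, power = Φ(ln 1.2 × √(D·a(1 − a)) − 1.960).

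- All 141,804 count: n = 225,472, a = 0.371, D = 1,172; 0.1823 × 16.54 − 1.960 = 1.056; power 85.5%.
- Half count: n = 154,570, a = 0.541, D = 804; 0.1823 × 14.13 − 1.960 = 0.616; power 73.1%.

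The same formula gives 81% if three quarters count and 55% if a quarter do. The 141,804 include patients with no inhaler at all, who are comparators under neither wording. The first line is therefore a ceiling, and these figures do not measure the gap between the two definitions.

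**The case against.** The best defence is that section M is the section on comparator groups and moves from a general sentence to cohort-specific ones. Section N's line could then be shorthand for both cohorts, to be read through section M's COPD sentence. That reading is reasonable, but section N does not refer back to section M and states a rule that can be programmed as it stands. The ambiguity remains.

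Other parts of the defence limit the point:

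- A reader might infer that section N admits any inhaler issued in the last 3 months. The text does not say that; the window belongs to the absence of ICS.
- A reader might infer that a patient with a LAMA two years ago and a reliever last month meets both definitions. Section M's closing sentence points to the same window for comparators as for ICS users, which undercuts that example. It does not settle which drugs count.
- The quoted rule belongs to the time-fixed option. Section N leaves the choice to the descriptive study and calls the time-updated approach preferable in theory. The drug list still matters there, because patients who move to a drug outside the study's list are censored.
- Propensity weighting, which includes prior exacerbations, and the planned bias analysis for severity may remove part of any bias. The exclusion of "people who are prescribed a LABA/LAMA and ICS within 3 months before the cohort entry date, as this indicates severe COPD" takes patients labelled severe out of the ICS group, which would work against an apparent harm.

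**Conclusion.** The inconsistency is real and can be read directly from sections M and N. It should be settled before the comparative analyses, but it is an unresolved definition and not a demonstrated bias.

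A reader might conclude that the wording will make ICS look harmful. The documents do not support that. They do not say that reliever-only patients have a lower COVID-19 hazard, they do not give the share of such patients, and section P says that the effect of asthma and COPD on COVID-19 outcomes is not fully understood. The 1.02 to 1.25 range rests on an assumed share of 10-40% and an assumed relative hazard of 0.5-0.8, before adjustment. Its upper end passes the 1.2 that section K says the COPD cohort can detect for a positive test, so the choice of definition could matter.

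Comparison with the published figures in section C needs care. The 1.13 and 1.15 compare ICS users with the general population not using ICS. Only the 1.39 is a COPD contrast against LABA-LAMA.

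**What to change.** - **Section N, time-fixed rule:** split the comparator by cohort. For COPD: no ICS, and at least one LABA and/or LAMA prescription, both judged in the 3 months before cohort entry that are used for ICS. COPD patients with only short-acting inhalers in that window enter neither group. The asthma drug list stays as it is.
- **Section M:** align the opening paragraph with the cohort-specific sentences and state the window.
- **Time-updated option:** use the same COPD drug list to decide when a patient has moved to a drug outside the study and is censored.

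This adopts the protocol's own COPD definition and costs a few sentences and a change to the code list. The downside is a smaller COPD comparator. Section K's claim of a detectable hazard ratio of 1.2 for a positive test should be rechecked against a count of COPD patients without ICS who have a LABA and/or LAMA in the window. Section J does not give that count.

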D. Aims, objectives, rationale

The aim of this study is to investigate the effects of ICS at different stages of the COVID-19 disease pathway (i.e., infection, hospitalisation, and death) among patients with asthma or COPD and apply methods of QBA to these effect estimates to account for potential biases arising in these estimates of association. The null hypothesis is that use of ICS has no effect on COVID-19-related outcomes.

Objectives

- A. To describe prescription patterns of ICS among patients with respiratory diseases before and during the COVID-19 pandemic.
- B. To investigate the association between prevalent ICS use and COVID-19 related outcomes among patients with respiratory diseases.
 - a. Estimate the association between prevalent ICS use and risk of having a positive SARS-CoV-2 test.
 - b. Estimate the association between prevalent ICS use and risk of hospitalization with COVID-19 among patients with a positive SARS-CoV-2 test.
 - c. Estimate the association between prevalent ICS use and risk of death among patients who were hospitalized with COVID-19.
- C. To develop approaches and apply methods of QBA to account for potential biases arising in these estimates of association.
 - a. Investigate impact of exposure misclassification (e.g., due to stockpiling of medication, patients not filling prescription or underascertainment of in-hospital medication use) on estimates from objective 2a, 2b, and 2c.
 - b. Quantify potential biases due to unmeasured or unknown confounders on estimates from objective 2a, 2b, and 2c.
 - c. Investigate impact of outcome misclassification (e.g., underascertainment of infections due to limited testing availability and non-random testing) on estimates from objective 2a.
 - d. Investigate impact of selection bias (e.g., non-random selection of individuals into a study) on estimates from objective 2b and 2c.

E. Outcomes

COVID-19 positive test result; hospitalisation with COVID-19; death with COVID-19, as defined in section N.

F. Study type

The overall study design is a historical cohort study.

G. Study design

Objective 1 will be a descriptive study with a population-level description of prescription patterns of ICS before and during the COVID-19 pandemic among patients with respiratory disease.

Objective 2 will be a hypothesis testing cohort study. The null hypothesis is that there is no association between ICS use and testing positive for COVID-19, hospitalisation for COVID-19 and death with COVID-19.

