Objective 3 will be a methodological study to develop and apply methods of quantitative bias analysis to account for potential biases arising in the estimates of the effects of ICS on COVID-19 outcomes.

H. Data source

This project will use the Clinical Practice Research Datalink (CPRD) Aurum, a database containing routinely collected patient data from GPs in the UK. CPRD Aurum includes data on 41 million patients (March 2022), with over 13 million patients currently registered (20% of the UK population).³¹ These patients come from over 1,300 GP practices which use EMIS GP patient management software.³¹ CPRD records information on diagnoses, symptoms, demographics and lifestyle factors, prescriptions, referrals, vaccinations and tests^{31,32}, coded using SNOMED and Dictionary of Medicines and Devices (DM+D) codes. CPRD Aurum has been shown to be broadly representative of the English population in terms of age, gender, geographical spread and deprivation.³²

I. Linked data

Data from CPRD can be linked to other databases such as the Hospital Episode Statistics (HES) and the Office for National Statistics (ONS) death registry. Both HES and ONS death registry data are linked to CPRD by NHS Digital using the NHS number, gender, date of birth and postcode.^{32,33} HES holds information on all patient contacts at NHS hospitals in England, with diagnoses recorded using International Classification of Disease 10th revision (ICD-10) codes.^{33,34} ONS death registry data contains information on all deaths occurring in England and Wales, including a cause of death documented using ICD-10 codes.^{34,35}

HES Admitted Patient Care will be used to identify hospitalisation with COVID-19. ONS death registration data will be used to identify death with COVID-19. Additionally, the Index of Multiple Deprivation (IMD) will be used as a covariate to adjust for socioeconomic deprivation, which has been associated with COVID-19 outcomes.³⁶

J. Feasibility counts

A feasibility count based on CPRD Aurum June 2021 build identified 225,472 patients with a COPD code before 29th February 2020, and 755,632 patients with an asthma code between 1st March 2017 and 29th February 2020. These patients were registered in CPRD on 1st March 2020 and had at least one year of registration prior to that date.

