before the previous one is estimated to have been completely used, we will assume stockpiling occurred and assign the maximum total days of exposure possible with the combined prescriptions. Patients who switch treatment groups will be considered exposed to the active comparator/ICS group from the date of the switch, and those who discontinue treatment or switch to a treatment not under study will be censored at discontinuation or switch.

Patients will be considered exposed from the date the prescription was issued, as ICS have been shown to exert anti-inflammatory effects within hours of administration.⁴³

Outcomes

- SARS-CoV-2 infection, defined as a recorded positive test for SARS-CoV-2 in the primary care record sourced from the Second Generation Surveillance System (SGSS).
- hospitalisation with COVID-19, defined as admission to hospital with an ICD-10 code for COVID-19, ascertained using HES data.
- death with COVID-19, defined as death with an ICD-10 code for COVID-19 listed as an underlying or contributing cause of death in the ONS death registry.

Covariates

- demographic and lifestyle variables at baseline: age, sex, body mass index (BMI), smoking status, ethnicity, socioeconomic status (Index of Multiple Deprivation, IMD)
- ever-present comorbidities at baseline: chronic kidney disease, hypertension, heart failure, other heart diseases, diabetes, cancer, immunosuppression
- time-updated covariates: influenza vaccination within one year before the cohort entry date, pneumococcal vaccination within 5 years before the cohort entry date, vaccination against COVID-19 (wave 2 only)
- calendar time, COVID-19 prevalence figures (ONS)
- asthma cohort only: number of recorded asthma exacerbations (emergency department visit, hospitalisation or prescription of an oral corticosteroid for asthma⁴⁴) within 1 year before the cohort entry date
- COPD cohort only: number of recorded COPD exacerbations (defined using a validated algorithm⁴⁵) within 1 year before the cohort entry date.

O. Data analysis

Descriptive study:

Population-level measures of ICS use that will be determined per calendar month are:

- Number and proportion of incident and prevalent users over the course of follow-up for each calendar month:
 - Prevalent ICS exposure will include people with an ICS prescription recorded on any day during that month.

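### If exposure is time-updated, the discontinuation rule in objective 2c censors patients still in hospital when their GP-issued supply plus gap runs out, and later deaths are not counted

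*Protocol*

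**What the plan says.** Objective 2c (item B.c in Protocol section D) is to "Estimate the association between prevalent ICS use and risk of death among patients who were hospitalized with COVID-19".

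Section N, Exposure, gives two options: "Exposure will be prescription of ICS, which may be determined in a time-fixed or time-updated manner". The choice is to follow the descriptive study.

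- Time-fixed: "Patients can then not switch between exposure groups, even if they initiate ICS or their ICS exposure ends". Nobody is censored because a supply ends.
- Time-updated: "ICS prescriptions in the year before the cohort entry date up until the end of follow-up will be used to ascertain exposure status". Each prescription is given a calculated length, overlapping supplies are carried forward, and a gap is allowed before the next prescription, with half a median duration as the example. At the end of this option, "those who discontinue treatment or switch to a treatment not under study will be censored at discontinuation or switch".

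The prescriptions come from CPRD Aurum, which section H describes as "a database containing routinely collected patient data from GPs in the UK". Objective C.a lists "underascertainment of in-hospital medication use" as a source of exposure misclassification for 2a, 2b and 2c. Section O plans inverse-probability of censoring weights if exposure is time-updated. Section M applies the same exposure calculation to the comparator group.

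**The concern.** The time-updated rule is written for people living at home who visit their GP. In 2c every patient enters by being admitted, and the rule runs unchanged through the stay. Two patients with identical supplies then fare differently. The one discharged before supply plus gap ends can renew and remains at risk. The one still in hospital has no visible renewal, is taken to have stopped and leaves the risk set. The second patient is on average the sicker one, so the censoring is related to the outcome. Deaths after long stays are not counted, and the later risk set is enriched with recovering patients.

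That in-patients do not renew GP prescriptions is not stated in the protocol. It is inferred from the GP data source together with the acknowledged under-recording of in-hospital medication.

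**Working it through.** **The plan's own figures.** The protocol gives no figure for in-hospital censoring and no sample size for 2c. Table 1 (section K) is reproduced by events = (1.960 + 0.842)² / (0.64 × 0.36 × ln(HR)²). For HR 1.4 this is 7.849 / 0.02608 = 300.9 events; divided by 0.0005 it gives 601,806, against 601,807 in the table. This serves only as a power reference below.

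**Inputs for the loss of deaths.**

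- Gap g: half the supply length L, the example in section N.
- Supply length: not in the documents; assumed 30, 60 or 90 days, a single prescription.
- Remaining supply at admission R: assumed uniform on 0 to L.
- Time from admission to in-hospital death D: assumed exponential with mean m = 8 or 12 days.

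**Formula.** Share of in-hospital deaths falling after censoring:

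P(D > R + g) = exp(−g/m) × (m/L) × (1 − exp(−L/m))

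| L, g (days) | m = 8 | m = 12 |
|---|---|---|
| 30, 15 | 0.1534 × 0.2604 = 4.0% | 0.2865 × 0.3672 = 10.5% |
| 60, 30 | 0.0235 × 0.1333 = 0.3% | 0.0821 × 0.1987 = 1.6% |
| 90, 45 | 0.0036 × 0.0889 = 0.03% | 0.0235 × 0.1333 = 0.3% |

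Time to death matters too. With Weibull times (shape 1 or 1.5) and medians of 7 to 21 days, the ranges with the gap widen to 2%–39% (30 days), 0%–16% (60 days) and 0%–7% (90 days).

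**When the censoring acts.** With L = 30 and g = 15, no in-patient is censored before day 15. By day 30 the share is (30 − 15)/30 = 50%, and by day 45 it is 100%. Early deaths are kept.

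**Can the planned weights correct it?** Weights correct for predictors that are in the censoring model. The covariates in section N are demographics, comorbidities, vaccinations, calendar time, COVID-19 prevalence and prior exacerbations. Neither current in-patient status nor in-hospital severity is listed. Beyond 1.5 × L, no in-patient with a single prescription remains uncensored, so there is nobody to weight up.

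**Can the bias analysis correct it?** Section P handles exposure misclassification through sensitivity and specificity, and details adherence and stockpiling. This reclassifies exposure; it does not restore a censored death. The selection-bias step concerns entry to the 2c population, not exit from it.

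**Effect on the hazard ratio.** Simulation with true HR 1, 64% exposed, 25% dying in hospital and mean stay 12 days, with discharged patients kept at risk:

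- 30-day supply in both groups: the HR stays within about 0.02 of the uncensored value.
- 30 days in one group and 60 in the other: with ICS on the shorter supply, the HR falls by about 0.06 to 0.08 with the gap and 0.11 to 0.14 with no gap. If the comparator has the shorter supply, the shift is upward.

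**Precision.** Taking 301 events as 80% power at HR 1.4, losing 5% of events gives 78.0% and losing 10% gives 75.7%.

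**The case against.** **The branch is conditional.** Time-updated exposure may not be chosen, and under the time-fixed option the problem does not arise. The gap is only an example, and operational detail may be set in an analysis plan not shown here. This stands and limits the weight of the point. However, section N calls time-updating preferable in theory and makes the choice turn on stockpiling, so it could be adopted without this consequence being noticed.

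**The loss may be negligible.** With 60- or 90-day supplies it is under 2% on the main assumptions, and carry-forward of overlapping supplies delays censoring further. If the descriptive study's six-month definition of discontinuation (section O) were used in the comparative study, almost nothing would be lost within the 184 days of wave 1. The protocol does not say that it applies there.

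A reader might also infer stronger points that the documents do not support:

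- *A quarter to a third of deaths are lost.* The figure of 26% to 37% needs a 30-day supply and no gap; section N says a gap would be permitted.
- *Censoring weights cannot help at all.* They are planned for exactly this option, and in-patient status could be added from HES dates. They are incomplete, not useless.
- *The HR is biased as the plan stands.* The same rule acts in both groups, and nothing in the protocol shows that supply lengths differ.
- *The loss falls on an already rare outcome.* Section K calls death rarest across the whole disease cohorts, not among hospitalised patients.
- *Objective 2b needs the same change.* Under section L its follow-up ends at the outcome, COVID-19 admission, so the in-patient time at issue is absent.

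**Conclusion.** The concern holds conditionally. If time-updated exposure is chosen, the rule as written produces informative censoring in 2c that the planned weights address only in part and the planned bias analysis does not undo. On the stated assumptions and the example gap, about 4% to 11% of in-hospital deaths are lost with 30-day supplies, 0.3% to 1.6% with 60 days and under 0.4% with 90 days. The assumptions on supply length and time to death drive the result, and the documents supply neither. Material bias in the HR requires supply lengths or refill patterns that differ between ICS and comparator inhalers; its direction is unknown. The point should be settled before the comparative analyses begin, but it does not undermine the design.

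**What to change.** Add to section N, under the time-updated option: (1) for objective 2c, the exposure group is held at its status on the admission date, with no switching and no discontinuation censoring after admission; (2) in any other analysis where time-updated follow-up spans an admission, HES in-patient days do not count toward supply or the allowable gap. No change to 2b is needed on this ground.

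The first change brings deaths lost to apparent discontinuation in hospital to zero in 2c and fits the stated objective, which concerns prevalent use. The cost is two sentences and some code using HES admission and discharge dates. The downside is that true inhaler changes after admission are not reflected in 2c; those made in hospital are not visible in the data anyway.
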